which is a return on investment of \$4.70 – 5.60 in future educational remediation, juvenile delinquency, teen pregnancy, substance abuse, and mental illness ^{xv}. Providing support to young moms in Forsyth County is something we cannot afford *not* to do.

Our project will address this emerging health crisis at a time when value-based care models as part of Medicaid transformation are rolling out throughout North Carolina and all programs have had to adapt to changing the delivery mechanisms to more remote offerings. During the pandemic, Imprints Care developed a hybrid model for provision of services through Parents as Teachers. Imprints Cares evidence-based Parents as Teachers hybrid model may have far reaching implications in establishing a pediatric value-based model that can be replicated throughout our community, state, and country. Since January 2021, Wake Forest Baptist Medical Center (WFBMC) has documented 82 births to young moms ages 14 through 21. Since July 2020 Imprints Cares family educators have received approximately 400 referrals from pediatricians with more than 320 families being served, 80%.

Further, as we are considering the intersection of equity with health and social policy, the YMP is an opportunity to directly address disparities in behaviors such as breastfeeding, completion of developmental screenings, and enrollment in early intervention that may be correlated with different demographic groupings. We know that while COVID-19 was traumatic for everyone, young children growing up in poverty were disproportionately impacted. The true impact of the pandemic and public health precautions (i.e., isolation) is just beginning to emerge. We continue to see increased trends in pregnancy in young moms, toxic stress and child maltreatment, food insecurity, and developmental/ behavioral regression in young children. As we enhance opportunities for young moms based on positive outcomes during the pandemic, we can rapidly embed responses to traumatic events into our approach. To the extent that some young moms are perpetuating a multi-generational pattern of early births, the proposed hybrid program is an opportunity to break a cycle linked to poor outcomes for young moms and their children.

Objectives

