The objectives of this study are to assess cost-effectiveness of a Young Moms Program that incorporates a traditional Parents as Teachers home visiting parenting program to that of a hybrid virtual/home based Parents as Teachers program, against short-term outcomes, which in turn will serve as leading indicators of longer-term results. Specific outcomes are outlined in the measures section.

Methods and Measures

This is a community-engaged research collaboration between the non-profit Imprints Cares, the WFBMC Birth Center, and WFSOM. Because YMP is a tiered program model, services meet parents where they are through a “warm hand-off” approach that uses on one-on-one consultation and assessment-based interventions. The YMP is designed to address systemic barriers to the health and stability of young moms and their children such as the lack of coordination of service delivery or logistical barriers within the health system. The YMP also streamlines the referral pipeline, connecting

Protocol version:

Template updated 9.24.14

moms to evidence-based resources, and ensuring children complete all recommended assessments prior to kindergarten.

This research project is a pilot randomized controlled trial. We expect a total of 30 participants, 15 in each arm of the study. For inclusion into this study participants must be an immediately post-partum mother, between 14-21 years of age who will reside with her newborn. The mother must be referred from either the Birth Center at Wake Forest Baptist Health or from one of the Wake Forest Baptist Health PPC partner practices. Exclusion criteria include that newborn of participating mothers must be ≥ 35 weeks of gestation and not have an extended NICU stay. These populations are excluded because medically complex newborns and a prolonged separation during the intervention period will directly affect our outcome measures. Participants must speak English or Spanish given our parent educators and other group participants are limited to those languages. Males are excluded as participants, the intervention and many of the outcome measures are only applicable to female participants.

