In addition to these assessments, the team will use an intake questionnaire to capture parent demographic and health information as well as baseline knowledge about child development and parenting and a monthly questionnaire used to assess mother's status on continuance of secondary education, breastfeeding, and use of contraception. A monthly questionnaire, which will be developed for use in this study, also will assess infant developmental milestones.

Further, the team will access health information captured in WFBMC's Epic system, including completion of Well-Child Visits and recommended immunizations. A WFBMC study team member will extract data on participants as well as a matched control group. The study team will conclude the study with participant focus groups, to collect additional qualitative feedback and insights. Finally, the team will develop and implement Fidelity of Implementation (FOI) quality

Protocol version:

Template updated 9.24.14

assurance guidelines and checklists to capture the degree to which project services are delivered as expected. FOI scores will be used as a predictive variable with the goal of establishing a minimum service threshold for short-term outcomes.

Proposed Statistical Analyses

Descriptive Analyses. All data will be subject to descriptive analyses, including measures of central tendencies and frequency distributions, as appropriate for the type of data collected. Descriptive analyses will support our understanding of participant characteristics and equivalency of samples in the traditional and hybrid models.

Inferential Analyses. Inferential analyses, such as t-tests, multiple regression, and Analysis of Variance, will be conducted to test for change between baseline and end-of-study data collections with the PHQ 9, and the PFS. The PFS will be administered at service week one, service week six, and at the end-of-study to assess differences between the models at promoting protective and nurturing behaviors. Tests also will be used to assess differences between the models on maternal outcomes such as continuance of secondary education, breastfeeding, and use of contraception and child-focused outcomes such as STIMQ2-I, completion of Well Child Visits and immunizations. The study team will work with CTSI Biostatistical Support services to advise and guide the analytic approach.

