Proposed Cost Effectiveness Study Design. One of the primary challenges of completing cost studies is fully accounting for all costs and benefits. Therefore, the study team will use this project period to identify the spectrum of costs associated with serving one young mother and her child. These data will be compiled to generate an average cost of service and establish outliers that exist when there are particularly risky or traumatic cases. In addition, the team will establish short-term benefits (achievable after six-months of services) along with the program implementation conditions necessary to achieve them. We will utilize the services of BERD and Q-Pro to assist in advising in areas of study design, data analysis, and data management.

Study Timeline

Study Milestone	M1	M2	M3	M4	M5	M6	M7	M8	M9	M10	M11	M12
Achieve IRB approval	•											
Enrollment of teen moms		•	•	•								
Baseline data collected		•	•	•								
Services delivered	•	•	•	•	•	•	•	•	•	•		
Week one data collected	•	•	•									
Week six data collected		•	•	•								
ASQ/ASQ-SE data collected (2,4, and 6m)			•	•	•	•	•	•	•	•	•	•
Monthly questionnaires and FOI checklists completed			•	•	•	•	•	•	•	•	•	
End of study data collected											•	•
Analysis and reporting completed												•

The project will track numerous milestones, including:

- Submission of IRB application and receipt of IRB approval. This milestone is critical as the project will not move forward without IRB approval.
- Enrollment of young moms by the project's four month. All participants will need to be enrolled by month four to ensure moms in both models can receive at least six months of home visitation services. In the traditional model, home visitation starts immediately upon

Protocol version:

Template updated 9.24.14

enrollment. In the hybrid model, home visitation starts at the completion of the six-week What You Do Matters virtual class.

- Collection of all baseline data. Baseline data will be collected at the time of enrollment and will consist of the enrollment form and the PHQ 9.
- Collection of week one and week six data. Data will be collected during the participant's first and sixth week (at the close of the What You Do Matters course) of services in both models (PFS).
- Collection of monthly questionnaires. Monthly questionnaires will be implemented with each participant, on a schedule developed by the family educator.

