- Collection of ASQ and ASQ:SE data as recommended by the publisher (2, 4, 6m).
- Collection of end-of-study data (6 months after enrollment). In the final month of services, the team will collect the ASQ, ASQ:SE, PHQ 9, the PFS and the StimQ2-I.
- Collection of FOI checklist data. Project staff and supervisors will complete FOI checklists on a monthly basis. Each model will have its own checklist.
- WFBMC data extraction and compilation of analysis files. One of the WFBMC team members will work to securely extract health data for treatment and matched control group participants from the Epic system.

Human Subjects Protection

Subject Recruitment Methods

No additional PHI will be accessed or printed/transcribed above and beyond what is part of standard patient care and pre-defined job descriptions.

OB Home Visiting Staff

- 1) Our OB Home Visiting Nursing Staff as part of their standard workflow identify and visit all post-partum mothers that reside in Forsyth County, NC.
- 2) Of those, they will identify mothers that meet inclusion criteria for the study (14-21 years old, Spanish or English Speaking, will reside with their newborn upon discharge, and will follow up with a Wake Forest Baptist Health Pediatrician).
- 3) During their standard meeting, while the mother is still inpatient from her delivery, OB home visiting staff per their standard workflow will ask if the mother would like referral to Imprints Cares. If they identify a likely eligible participant, they will introduce study at that time, without promising the patient they are eligible. If the patient is interested in referral for either the study or services not provided as part of the study, the team will make a referral to Imprints Cares. The referral will indicate if the patient appears to be eligible for the study or not.

Imprints Cares

- 1) After referral from the PPC primary care physician or the OB Home Visiting Nursing Staff to the Imprints Cares program, intake staff will assess if new mothers meet criteria for participation in the study (14-21 years old, Spanish or English Speaking, will reside with their newborn upon discharge, and will follow up with a Wake Forest Baptist Health Pediatrician).

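### The first two PFS assessments are timed by service receipt with no PFS at enrollment, and the end-of-study visit has three timings that disagree, so mothers who never start or who stop services can drop out of the comparison

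*Combined protocol and SAP*

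**What the plan says.** All references are to the combined protocol and SAP.

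- **PFS, Inferential Analyses:** "The PFS will be administered at service week one, service week six, and at the end-of-study to assess differences between the models". The same paragraph plans a test of change from baseline to end of study for the PHQ 9 and the PFS.
- **PFS, milestone list under Study Timeline:** the survey is taken in the "first and sixth week (at the close of the What You Do Matters course) of services in both models (PFS").
- **Baseline, same list:** data at enrollment are the enrollment form and the PHQ 9. The PFS is not among them.
- **End of study, same list:** the item opens with "Collection of end-of-study data (6 months after enrollment") and continues: "In the final month of services, the team will collect the ASQ, ASQ:SE, PHQ 9, the PFS and the StimQ2-I".
- **End of study, timeline table:** the row "End of study data collected" is marked in months 11 and 12. Services are marked through month 10 and enrollment in months 2 to 4.
- **Size, Methods and Measures:** "We expect a total of 30 participants, 15 in each arm of the study".

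The document names no analysis population. It gives no rule for following a mother who never starts or who stops services, and no handling of missing data.

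**The concern.** The stated objective is the cost-effectiveness of two service models against short-term outcomes. The models ask for different contact: two home visits a month in one, and a six-week virtual class followed by one visit a month in the other. Uptake and stopping may therefore differ by model, and that difference is part of what the trial should measure.

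If an assessment exists only for mothers in services, or its date moves with the length of service, the benefit of randomization is lost for that outcome. The model that loses more of its less engaged mothers would look better than it is. The plan also wants to use fidelity scores to find a minimum service threshold. That needs outcomes from mothers who received little service, and they are the ones most easily lost.

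**Working it through.** **1. Planned size.** The 30 participants (15 per arm) come without alpha, power, effect size, SD or drop-out, so the figure cannot be reproduced. It is used below only for scale.

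**2. PFS.** Three statements taken together settle this part.
- Baseline at enrollment has no PFS.
- The first PFS is in the first week of services.
- The change test needs a baseline PFS.

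The service-week-one PFS is thus the only possible baseline. A mother with no service week one has none, and has no week-six value either. This follows from the stated rules and needs no assumption.

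**3. End-of-study dates.** Enrollment is in project months 2-4.

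| Timing rule | Arithmetic | Project month |
|---|---|---|
| 6 months after enrollment | 2 + 6 to 4 + 6 | 8-10 |
| End of services, hybrid, if home visits last six months after the six-week class | 2 + 1.5 + 6 to 4 + 1.5 + 6 | 9.5-11.5 |
| Timeline table | as marked | 11-12 |

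The table's months fall between 11 - 4 = 7 and 12 - 2 = 10 months after enrollment, not at 6. The second row applies only if at least six months of home visits is meant for both models, as the enrollment milestone suggests. In that case the service-based date falls about six weeks later in hybrid than in traditional, at an older infant age. Mothers may also continue in the program until the child enters kindergarten, so the last month of services needs a definition in any case.

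**4. Possible bias (assumed inputs).** Let a fraction s of an arm stop, and let stoppers score g SD below those who stay. The mean of those who stay exceeds the whole-arm mean by s × g. With no true difference between models and the same g in both arms:

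bias = (s₂ - s₁) × g

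- s₁ = 0, s₂ = 0.20 (3 of 15), g = 0.5: 0.20 × 0.5 = 0.10 SD
- s₁ = 0, s₂ = 0.20, g = 1.0: 0.20 × 1.0 = 0.20 SD
- s₁ = 0.10, s₂ = 0.30: again 0.10 to 0.20 SD
- s₁ = s₂ = 0.20: 0 SD

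**5. Scale.** With 15 per arm the standard error of a difference in means is √(2/15) = 0.37 SD. At an assumed two-sided 5% level and 80% power, the detectable difference is (1.960 + 0.842) × 0.365 = 1.02 SD. If 20% per arm are not assessed, n = 12 and it is 2.802 × √(2/12) = 1.14 SD.

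**The case against.** A reader might infer that a mother who stops services has no outcome visit at all and that the trial is therefore a comparison of service completers. The documents do not support that.

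- The end-of-study item gives an enrollment-based date immediately before the sentence on services. The fault there is conflict, not absence.
- The table places end-of-study collection after services end, which counts against the view that data are taken only during services.
- No passage restricts the analysis to completers. The risk comes from silence.
- Several outcomes do not depend on service timing: the baseline PHQ 9, the 2- and 4-month ASQ and ASQ:SE, and the well-child visits and immunizations taken from the health record. Monthly questionnaires go to each participant, although the family educator sets their schedule.
- It is also tempting to picture a site doing the end-of-study visit at month 3 for a mother who stops then. That would ignore both the six-month date and the five-month lower age limit given for the StimQ2-I. Being missed altogether is the more realistic outcome.
- The 80% in the background (320 of about 400) is uptake among referrals, so it says nothing about retention after randomization.
- The illustrative bias is at most about half a standard error (0.20/0.37 = 0.54), in a pilot that makes no power claim.

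All of this stands and narrows the point. It does not supply a PFS baseline for a mother who never starts, bring the three dates together, or say that those who stop are followed.

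**Conclusion.** The concern holds in a limited form. For the PFS, the timing rules as written exclude never-starters from the change test. For the end-of-study visit, three timings disagree, by one to four months between the six-month rule and the table (7 to 10 months against 6). With no follow-up or analysis rule, mothers who stop may be missed or assessed at a different time. The outcomes exposed are the PFS, the end-of-study PHQ 9 and the StimQ2-I.

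The bias could be 0.10-0.20 SD if stopping differs by 20 points and the gap is 0.5-1.0 SD. It is 0 if stopping and the gap are equal in both arms. The stopping rates and the gap are assumptions; the documents give no basis for either. A bias of this size is small beside the sampling error at 15 per arm. It is systematic, however, and it would enter the effect estimates that the pilot is meant to produce. The plan should be changed before enrollment because the correction is cheap.

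**What to change.** In Inferential Analyses, the timeline table and the milestone list:

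1. Time the PFS from enrollment or randomization, the same in both arms: first week (taken at or just after enrollment, so that it serves as the baseline) and sixth week.
2. Set all end-of-study instruments at 6 months after enrollment or randomization. Delete the final month of services as a timing rule.
3. Correct the table row to match: months 8-10 for enrollment in months 2-4. Reconcile the stated length of home visiting in each model with the services row; this point takes no view on what that length should be.
4. Add a rule such as: these assessments are collected from every randomized mother, remotely if needed, whether or not she started or stopped services, and she is analyzed in her assigned model.
5. Check that the consent form, which is held with the IRB application, allows contact after services stop.

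The cost is a wording change and a few extra remote contacts with mothers who may be hard to reach. The effect estimate will then include non-users of the service, which suits a comparison of models as offered. Any analysis by amount of service received can be reported beside it.

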Appendix (see relevant sections of IRB application)

1. Data collection form
2. Copies of each questionnaires or surveys that will be used
3. Consent form if one will be used
